4.3. Secondary Endpoint(s)

4.3.1. Pharmacokinetics

4.3.1.1. Estimands

Table 3 Primary Estimand for Secondary Pharmacokinetics Endpoint (Part A)

Primary Estimand	
Population	Male or female healthy participants aged 18 to 65 years who would be able to complete the IM dose
Variable/Endpoints	
 • AUC_{D1-29} and C_{max} through Day 29 • AUC_{inf} through Week 24 • Serum PK of sotrovimab through Day 29 and Week 24
Treatment Conditions	
 • AUC_{D1-29} and C_{max} through Day 29: 100 mg/mL sotrovimab (anterolateral thigh, deltoid) vs 62.5 mg/mL sotrovimab (dorsogluteal) • AUC_{inf} through Week 24: 100 mg/mL IM sotrovimab at three injection sites (dorsogluteal, anterolateral thigh, and deltoid) compared to the 62.5 mg/mL formulation administered dorsogluteally • Serum PK of sotrovimab through Day 29 and Week 24: 100 mg/mL and 62.5 mg/mL IM sotrovimab

Primary Estimand	
Strategy for Intercurrent Events or Events Leading to Missing Data	The intercurrent event of interest is participants receiving an incomplete IM dose. The strategy for handling this intercurrent event will be a Principal Stratum Strategy, where we are only interested in the strata of participants who would be able to receive a complete IM dose. Exclusion of participants who did not receive a complete IM dose will not introduce bias as the reasons for dose interruption are not related to their PK.
Population-Level Summary	
 • AUC_{D1-29} and C_{max} through Day 29: The point estimate for the ratio of the geometric mean of 100 mg/mL treatment group compared to the 62.5 mg/mL treatment group and the related 90% CI will be calculated • AUC_{int} through Week 24: The point estimate for the ratio of treatment group geometric means and the related 90% CI will be calculated • Serum PK of sotrovimab through Day 29 and Week 24: Geometric mean

Table 4 Primary Estimand for Secondary Pharmacokinetics Endpoint (Part C Cohort 1)

Primary Estimand	
Population	Male or female healthy participants aged 18 to 65 years who would be able to complete the IV dose
Variable/Endpoints	
 • AUC_{D1-29} and C_{max} through Day 29 • Serum PK of sotrovimab through Day 29 and Week 24
Treatment Conditions	
 • AUC_{D1-29} and C_{max} through Day 29: Single IV infusion of sotrovimab at 3000 mg dose • Serum PK of sotrovimab through Day 29 and Week 24: Single IV infusion of sotrovimab at 3000 mg dose
Strategy for Intercurrent Events or Events Leading to Missing Data	The intercurrent event of interest is participants receiving an incomplete IV dose. The strategy for handling this intercurrent event will be a Principal Stratum Strategy, where we are only interested in the strata of participants who would be able to receive a complete IV dose. Exclusion of participants who did not receive a complete IV dose will not introduce bias as the reasons for dose interruption are not related to their PK.
Population-Level Summary	
 • AUC_{D1-29} and C_{max} through Day 29: Geometric mean

Primary Estimand	
	
• Serum PK of sotrovimab through Day 29 and Week 24: Geometric mean

4.3.1.2. Definition of Endpoint(s)

Serum concentrations will be listed and summarized using descriptive statistics. Positive pre-dose concentrations, post-dose samples below the limit of quantification (BLOQ) will be excluded from summary statistics.

Serum pharmacokinetic parameters will be calculated by standard non-compartmental methods using the currently supported version of WinNonlin (currently version 8.3.1.)

Calculations of pharmacokinetic parameters for the analysis will be based on actual sampling times. Pharmacokinetic parameters listed in [Table 5](#) will be determined from the serum concentration-time data, as data permits. If parameters cannot be determined, a 'Not done' or 'Not calculable' flag will be present in the data.

AUC will be computed using the log down, linear up trapezoidal rule. Where $\%AUC_{exp} > 20\%$, AUC_{inf} and all related parameters (i.e., CL/F , Vz/F , variance) will be presented in listings but excluded from the calculation of summary statistics. The decision as to which data points describe the terminal phase will be reached by inspecting the semilogarithmic plot of the data, only considering concentrations at time points beyond T_{max} . A minimum of 3 data points will be used for the estimation of λ_z . For poorly estimated λ_z (i.e., a span of <2 half-lives or $R^2 \leq 0.80$), the corresponding $t_{1/2}$ values will be excluded from summary statistics. C_{max} and T_{max} will be presented in listings but excluded from the calculation of summary statistics if there is insufficient data from the absorption phase (IM) or the end of infusion (IV). Any parameters for which estimates are available in fewer than 3 participants per treatment group will be excluded from descriptive statistics.

PK data from this study may be combined with data from other studies for the purpose of PopPK model development. Details of any future analyses and results will be provided in a separate PopPK analysis plan and report, if applicable.

Table 5 Derived Pharmacokinetic Parameters

Parameter	Parameter Description
%AUC _{exp}	Percentage of AUC _{INF} due to extrapolation from T _{last} to infinity
λ _z	Terminal elimination rate constant
AUC _{D1-29}	Area under the concentration-time curve from study Day 1 to Day 29.
AUC _{last}	Area under the serum concentration-time curve from time zero to time of last measurable (positive) concentration
AUC _{inf}	Area under the plasma concentration-time curve from time zero to infinity
CL (IV) CL/F (IM)	Apparent total clearance
C _{max}	Maximum observed serum concentration, determined directly from the concentration-time data.
C _{last}	The last observed quantifiable serum concentration
T _{max}	Time to reach C _{max} , determined directly from the concentration-time data.
t _½	Terminal elimination half-life will be calculated as: $t\frac{1}{2} = \ln 2 / \lambda z$
T _{last}	Time to reach the last quantifiable concentration
V _z (IV) V _z /F (IM)	Apparent volume of distribution will be calculated as: $Vz/F = \frac{CL/F}{\lambda z}$

NOTES: Additional parameters may be included as required. The parameters to be included in each in OPS.

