	PIN_TS3.0 ⁷			X	X	X	X	X						10. Hematology assessments will be performed only on Days -1, 2, 5, 8, and 29.
	Pain-NRS ⁸			X	X	X	X	X						11. Screening and Day -1 tests must be >24 hours apart.
	Safety laboratory assessments (hematology ¹⁰ , clinical chemistry, coagulation)	X	X ⁹	X		X	X		X	X	X		X	12. Urine or serum pregnancy test, as per local guidelines. See Section 8.3.5.
Sample collection	Urinalysis and urine albumin to creatinine ratio	X	X				X	X	X	X			X	13. Day 1 sample collection will occur pre-dose, and at 1, 2, 6, 8, 24 (Day 2), and 48 (Day 3) hours after the first injection. On other days, samples will be collected once at any time during the day.
	Urine drug/alcohol screening	X		X										
	HIV, Hepatitis B and C screening	X												
	SARS-CoV-2 molecular test ¹¹	X	X											
	Pregnancy test ¹²	X	X										X	
	Blood sample for PK analysis ¹³			X ¹³	X	X	X	X	X	X	X	X		
	Blood sample for immunogenicity testing (ADA and drug-neutralizing antibody)			X ¹⁴					X		X	X	X	
CCI														
AE review														
SAE review	X ¹⁵	X ¹⁵												

AESI and concomitant medication review		<===== X =====>	
14. On Day 1, sample collection will occur pre-dose.15. At Screening and on Day -1, only SAEs related to study participation or a GSK product will be reported.16. If participant withdraws early from the study prior to Week 24, then the W24 visit assessments will be performed as the ED/EW visit. If the participant withdraws early from the study after Week 24, the W35 visit assessments will be performed as the EW visit.
----------------------------------------	--	-----------------	---------------------------------------------------------------------------------------------------------------------------------------------------------------------------------------------------------------------------------------------------------------------------------------------------------------------------------------------------------------------------------------------------------------------------------------------------------------------------------------------------------

Table 2 Schedule of Activities: Part C

Study Visit Day ± Visit Window	Screening ¹ (up to Day -28)	W1			W2	W3	W4	W8	W12	W20	W24	W35	COVID-19 Test	Notes ¹³	
		Day -1	Day 1	Day 2											

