3. ANALYSIS SETS

Analysis Set	Definition / Criteria	Analyses Evaluated
Screened	All participants who were screened for eligibility.	
 • Study Population
Enrolled	
All participants who entered the study.
 
Note: screening failures (who never passed screening even if rescreened) are excluded from the Enrolled analysis set as they did not enter the study.
	
 • Study Population (Part C)
Randomized	All participants who were randomly assigned to study intervention.	
 • Study Population (Part A)
Safety	All randomized (Part A)/ enrolled (Part C) participants who were exposed to study intervention. Participants will be reported according to the intervention they actually received.	
 • Safety • Study Population • PRO Assessments • CCI [REDACTED]
Pharmacokinetic (PK)	
All participants in the Safety analysis set who had at least 1 non-missing PK assessment – i.e., PK sample collected and analyzed. Note: Non-quantifiable [NQ] values will be considered as non-missing values.
 
Participants will be reported according to the intervention they actually received.
	
 • PK • Safety
PK Principal Stratum	All participants in the PK analysis set who would be able to complete the IM/IV dose. Participants will be reported according to the treatment arm they actually received.	
 • PK • Safety

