4. STATISTICAL ANALYSES

4.1. General Considerations

4.1.1. General Methodology

All data will be reported for each study part separately, and separately for each Cohort within Part C. The data will be listed and summarized according to GSK reporting standards, where applicable. In summary tables, results will be presented by treatment arms. The treatment display format is specified in (OPS) Section 4.2.1 Study Treatment Display Descriptors.

Confidence intervals will use 95% confidence levels unless otherwise specified.

Unless otherwise specified, endpoints defined in Section 1.1 will be summarized using descriptive statistics, graphically presented (where appropriate) and listed. Continuous data (except for PK concentration data) will be summarized using n, mean, standard deviation (SD), median, minimum and maximum; for PK concentration data, between-subject CV (%CV_b), 95% CIs, 5th and 95th percentiles will also be reported along with above mentioned summary statistics; categorical variables will be summarized using n and percentage of participants in each category; log_e-transformed serum concentration and PK parameters will be summarized using geometric mean, 95% CI, SD (logs) and the %CV_b based on geometric mean. To assess relative bioavailability, log_e-transformed PK parameters will be statistically analyzed separately using Analysis of covariance (ANCOVA) Model to report point estimate for the ratio of the geometric means of treatment groups under comparison along with 90% CI.

In the case of a difference between the stratification assigned at the time of randomization and the data collected in the electronic case report form (eCRF), the analyses will be performed based on the data collected in the eCRF, not the assigned stratum at randomization.

For all study parts, JSRT will review safety data at regular intervals as described in the JSRT charter. During review of the Part A Sentinel cohort, the JSRT will review the participant data after all of the arms within a study Part have approximately 5 participants who have completed at least Day 8. This will include at least AE, SAE, AESI (including injection site reactions [ISRs]) and safety lab results. In Part A, an interim analysis (IA) will be conducted to review Part A data and decide whether to open Part B and, if needed, the selection treatment arms Part B; In Part C, an IA will be performed to support periodic data reviews across the program. Refer to Section 4.5 for more details.

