4.3.1.3. Main Analytical Approach

The secondary pharmacokinetic analyses will be based on the PK analysis set in all study parts, unless otherwise specified. Available data will be analyzed as collected regardless of intercurrent events that may occur (treatment policy). Missing data will not be imputed.

Drug concentration measures

Concentrations of sotrovimab in serum through Day 29 and Week 24 will be listed for all participants by actual time and summarized by treatment arm, concentration and nominal time. Standard summary statistics will be calculated (i.e. n, arithmetic mean, 95% CI, standard deviation, median, minimum, maximum, %CV_b, 5th and 95th percentiles). Refer to the R&D Guideline: Non-Compartmental Analysis of Pharmacokinetic Data, GUI_000722 (v6.0), for more information regarding the treatment of serum concentrations that are BLOQ.

Individual serum concentration-time profiles and median/mean profiles by treatment arm and by concentration will be plotted for each participant within one figure both on the untransformed scale (i.e. a linear plot) and on the log transformed scale (i.e. log-linear plot). See [OPS](#) Section 2 List of Data Displays/ TFL Table of Content for details.

Derived Pharmacokinetic Parameters

Parameters will be summarized according to the method defined in Section [4.3.1.1](#) as described below. Individual participant PK parameter values and a descriptive summary will be reported by treatment arm (for all study parts) and by concentration (for Part A only). Data display specifications for derived PK parameter summaries and listings are provided in [OPS](#) Section 2 List of Data Display/ TFL Table of Content.

Table 6 Summary Statistics for Transformed and Untransformed PK Parameters

Untransformed Data: all parameters	n, arithmetic mean, 95% CI for the arithmetic mean, SD, median, minimum, maximum, %CV _b (percent coefficient of variation between subjects)
Log _e -transformed Data: all parameters except for T _{max} , T _{last} , t _{1/2} , and λ _z	n, geometric mean, 95% CI for the geometric mean, SD of log _e -transformed data and %CV _b

The following statistical analyses will also be performed for the following derived PK parameters from evaluable participants. Evaluable participants are defined as those who have sufficient PK concentration data to allow estimation of PK parameters used for secondary endpoint analysis (i.e., AUC_{D1-29} and C_{max}).

Part A:

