5. SAMPLE SIZE DETERMINATION

The planned sample sizes for the number of evaluable participants in each treatment arm in Part A are based on precision estimation (using width of 90% CI) to assess the relative bioavailability. A sample size of approximately **50 evaluable participants** is selected for the two dorsogluteal arms in Part A (i.e., 500 mg IM of 62.5 mg/mL and 100 mg/mL sotrovimab arms, respectively) and approximately **25 evaluable participants** is selected for each of the 100 mg/mL sotrovimab anterolateral thigh and deltoid arms in Part A. Therefore, the total number of evaluable participants planned in this study is **150 in Part A**. To account for an expected 20% rate of non-evaluable participants approximately 190 participants will be randomized into Part A.

Sample size determinations are based on an assumed between participant CV_b for AUC_{D1-29}, AUC_{inf}, and C_{max} of 50%.

For the primary PK objective, assuming a point estimate of 1 for the ratio of each **primary PK endpoints** (i.e., AUC_{D1-29} and C_{max}) between the treatment arms under the variability assumptions and the planned sample size of evaluable participants described above, the 90% CIs are predicted to be:

Parameters	Treatment Comparison	Sample Size	CV _b	90% CI
AUC _{D1-29} and C _{max}	100 mg/mL sotrovimab dorsogluteal arm vs 62.5 mg/mL sotrovimab dorsogluteal arm	50 per arm	50%	(0.85, 1.17)

Similarly, for the secondary PK objective, assuming a point estimate of 1 for the ratio of each **secondary PK endpoints** (i.e., AUC_{D1-29}, AUC_{inf} and C_{max}) between the treatment arms under the variability assumptions and the planned sample size of evaluable participants described above, the 90% CIs are predicted to be:

Parameters	Treatment Comparisons	Sample Size	CV _b	90% CI
AUC _{D1-29} and C _{max}	100 mg/mL sotrovimab anterolateral thigh or deltoid arm vs 62.5 mg/mL sotrovimab dorsogluteal arm	25 vs 50	50%	(0.80, 1.25)
AUC _{inf}	100 mg/mL sotrovimab dorsogluteal arm vs 62.5 mg/mL sotrovimab dorsogluteal arm	50 per arm	50%	(0.85, 1.17)
AUC _{inf}	100 mg/mL sotrovimab anterolateral thigh or deltoid arm vs 62.5 mg/mL sotrovimab dorsogluteal arm	25 vs 50	50%	(0.80, 1.25)

Part C

The planned sample size for the number of evaluable participants in Part C Cohort 1 is 200. With 200 participants (intend to target up to approximately 20 Japanese

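### Dropping post-dose BLOQ samples overstates the descriptive serum concentrations at any time point where they occur; the SAP should keep, rank and count them

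*SAP*

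**What the plan says.** SAP 4.3.1.2 gives the rule for the concentration summaries: "Positive pre-dose concentrations, post-dose samples below the limit of quantification (BLOQ) will be excluded from summary statistics". It sets no limit by time point or by the share of samples that are BLOQ.

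The summary measure is fixed elsewhere. The estimand tables for Part A and Part C (SAP 4.3.1.1, Tables 3 and 4) give "Serum PK of sotrovimab through Day 29 and Week 24: Geometric mean", and SAP 4.1.1 says that log-transformed "serum concentration and PK parameters will be summarized using geometric mean". The list of concentration statistics in SAP 4.3.1.3 begins with "n, arithmetic mean, 95% CI, standard deviation, median, minimum, maximum" and goes on to the between-subject CV and the 5th and 95th percentiles. It names neither the geometric mean nor a count of BLOQ samples. The same section refers to a company guideline on non-compartmental analysis "for more information regarding the treatment of serum concentrations that are BLOQ", without saying whether that guideline or 4.3.1.2 prevails.

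For membership of the PK analysis set, SAP Section 3 says that "Non-quantifiable [NQ] values will be considered as non-missing values".

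In Part A, PK sampling starts early. Protocol 1.3, Table 1, note 13, with times counted from the initial injection: "Day 1 sample collection will occur pre-dose, and at 1, 2, 6, 8, 24 (Day 2), and 48 (Day 3) hours".

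**The concern.** A BLOQ result tells us that the concentration was low. If it is removed, the statistics at that nominal time describe only participants whose drug level was already measurable. The geometric mean, median and lower percentiles rise, and the reported minimum cannot fall below the LLOQ.

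The effect need not be equal across arms. Part A injects at three sites and samples at 1, 2, 6 and 8 hours. If one site absorbs more slowly, more of its early samples are BLOQ, more of its low results are dropped, and its mean or median profile is drawn closer to the faster arm. With no BLOQ count in the specified statistics, the summary table does not separate a missed sample from a low one. At stake is the description of the early absorption phase within the secondary serum PK endpoint.

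**Working it through.** **Inputs.** The between-participant CV of 50% comes from SAP Section 5, which states it for AUCD1-29, AUCinf and Cmax only. The documents give no CV for concentrations at 1 to 8 hours, no LLOQ, no expected BLOQ share and no absorption rate by site. These are assumed below, and a CV of 100% is shown beside 50%.

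**Scale check on the plan's own figure.** On the log scale SD = √ln(1 + CV²), as in SAP 6.2.2. At CV 50%, SD = √ln 1.25 = 0.472; at CV 100%, SD = √ln 2 = 0.833. For 50 vs 50 participants the 90% CI is exp(±1.661 × 0.472 × √(2/50)) = (0.855, 1.170). The SAP states (0.85, 1.17), so the lognormal reading of the CV is confirmed.

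**Bias at one nominal time.** Let f be the BLOQ share, z_f the standard normal quantile at f, and φ the normal density.

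- Geometric mean after exclusion, relative to truth: exp[SD·φ(z_f)/(1−f)]. Example, f = 30% at CV 50%: exp(0.472 × 0.348/0.70) = 1.26.
- Median after exclusion: the retained median is the (1+f)/2 quantile of the full distribution, so the ratio is exp[SD·z at (1+f)/2]. Example, f = 30%: the 65th percentile, exp(0.472 × 0.385) = 1.20.
- Geometric mean with LLOQ/2 substituted: exp[f·(SD·z_f − ln 2) + SD·φ(z_f)].

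In the table, each cell gives CV 50% / CV 100%.

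| BLOQ share | Geometric mean, excluded | Median, excluded | Geometric mean, LLOQ/2 |
|---|---|---|---|
| 10% | +10% / +18% | +6% / +11% | −5% / −3% |
| 30% | +26% / +51% | +20% / +38% | −11% / −5% |
| 50% | +46% / +94% | +38% / +75% | −15% / −1% |

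At f = 2%, exclusion gives +2% / +4%.

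**Two arms.** Take CV 50%, a true slow-to-fast ratio of 0.50 at an early time, and 5% BLOQ in the fast arm. The slow arm then has 43% BLOQ. The inflation factors are 1.384 (slow) and 1.053 (fast), so the displayed ratio is 0.50 × 1.384/1.053 = 0.66. With a true ratio of 0.80 it becomes 0.85.

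**Could BLOQ samples occur?** Protocol 4.3 predicts a Cmax of 912 µg/mL after 3000 mg IV. Under dose proportionality, 500 mg gives 152 µg/mL. The assumed early IM curve is C(t) = 152 × (1 − exp(−ka·t)), with complete bioavailability, no lag, an absorption half-life of 1 to 8 days and a CV of 50 to 100%. The BLOQ shares across these scenarios are:

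| Assumed LLOQ | 1 h | 2 h | 6 h | 24 h |
|---|---|---|---|---|
| 0.1 µg/mL | 0 to 2% | below 1% | 0% | 0% |
| 1 µg/mL | 0.1 to 90% | 0 to 46% | 0 to 8% | up to 0.1% |
| 5 µg/mL | 57 to 100% | 13 to 100% | 0 to 82% | 0 to 13% |

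At 0.1 µg/mL the largest bias is about +4%. At 5 µg/mL the worst case at 24 h is +23%.

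**Late times.** With a half-life of about 48.8 days (Protocol 10.9, rationale for Amendment 1), 2^(−28/48.8) = 67% of the peak remains after 28 days and 2^(−168/48.8) = 9.2% at Day 168. That is about 14 µg/mL at full bioavailability and 7 µg/mL at half. Little BLOQ is expected at Day 29. At Week 24 it is unlikely unless the LLOQ is at the upper end of the assumed range.

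**Reach into the PK parameters.** SAP 4.3.1.2 derives parameters from each participant's own concentrations at actual sampling times, not from the summarised means. The first 8 hours are 8/672 = 1.2% of the 28-day window.

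**The case against.** The strongest reply is that the documents do not show that any bias will occur. With a sensitive assay the BLOQ share may be 2% or less even at 1 hour, and the rule then hardly matters. That stands, and it makes the point conditional.

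A reader might go further in three ways that the documents do not support.

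- One might infer that the site comparisons are distorted. The planned contrasts use AUCD1-29, Cmax and AUCinf in ANCOVA models (SAP 4.2.1.3 and 4.3.1.3). Early concentrations are descriptive, with no between-arm contrast planned, so the two-arm example bears only on how the profiles look.
- One might infer that the SAP contradicts itself, because non-quantifiable values count as non-missing in Section 3. That sentence decides who belongs to the PK set. It is not a rule for summaries.
- One might infer that the guideline cited in 4.3.1.3 sets a conflicting rule. It is not among the documents and is cited for further information. What is missing is a statement of precedence; a conflict is not shown.

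It is also fair that any BLOQ rule is a convention: a geometric mean cannot contain zeros, and LLOQ/2 is itself biased. At CV 50% that bias is downward and smaller than the bias from exclusion (0.95 against 1.10 of the true value at 10% BLOQ, 0.85 against 1.46 at 50%). Finally, individual listings and n by time point are planned, so a loss of samples would be partly visible, though not its cause.

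**Conclusion.** The point holds as a conditional, descriptive one. At any nominal time with post-dose BLOQ samples, the rule in SAP 4.3.1.2 overstates the geometric mean, median and lower percentiles, and does so more in an arm with more BLOQ samples. The size depends on the BLOQ share. In the geometric mean it is +10%, +26% and +46% at 10%, 30% and 50% BLOQ if the CV is 50%, about +18%, +51% and +94% if it is 100%, and at most about +4% when BLOQ is about 2% or less.

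These figures assume lognormal early concentrations; the CVs and BLOQ shares are illustrations. In the scenarios tried, the effect falls mainly in the first hours after IM dosing and needs a sufficiently high LLOQ. The documents do not support saying that the secondary serum PK geometric means as a whole are biased. AUCD1-29, Cmax, AUCinf and the formal relative-bioavailability results are not shown to be affected. This is a minor improvement, worth making because it costs little.

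**What to change.** Replace the BLOQ part of the sentence in SAP 4.3.1.2 with a rule along these lines:

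- Post-dose BLOQ samples stay in the concentration summaries. For the median and percentiles they rank lowest (value 0); state the value used for the arithmetic mean as well.
- The geometric mean uses one named convention, either LLOQ/2 or a censored-lognormal estimate. If LLOQ/2 is chosen, note its downward bias, which at CV 50% is smaller than that from exclusion. Suppress the geometric mean when more than half of the samples in an arm at that time are BLOQ.
- Tables show n and the number BLOQ by arm and nominal time.

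In 4.3.1.3, add the geometric mean and the BLOQ count to the list of statistics, and say whether this rule or the cited guideline prevails.

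The cost is a few lines of SAP text and one table column, with no change to data collection or to the ANCOVA models. If BLOQ proves rare, the results hardly change.
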